# 7.7. Long Term Follow-up Evaluations (±14 days)

Subjects will continue to be followed for survival every 3 months for 24 months after registration.

## 8. CRITERIA FOR DISEASE EVALUATION

Response assessments for subjects with visceral/visceral plus bone disease will be made using RECIST v1.1. Response assessments for subjects with bone only disease will be made using MDA criteria.

# 8.1. Definitions Associated with Response Evaluation Criteria in Solid Tumors (RECIST) version 1.1

- **8.1.1. Measurable disease:** The presence of at least one measurable lesion. If the measurable disease is restricted to a solitary lesion, its neoplastic nature should be confirmed by cytology/histology.
- **8.1.1.1.** *Measurable lesions:* Measurable lesions are defined as those that can be accurately measured in at least one dimension (longest diameter to be recorded) as ≥20 mm by chest x-ray, as ≥10 mm with CT scan, or ≥10 mm with calipers by clinical exam. All tumor measurements must be recorded in millimeters (or decimal fractions of centimeters).
- **8.1.1.2.** *Non-measurable lesions:* All other lesions (or sites of disease), including small lesions (longest diameter <10 mm or pathological lymph nodes with ≥ 10 to <15 mm short axis), are considered non-measurable disease. Bone lesions, leptomeningeal disease, ascites, pleural/pericardial effusions, lymphangitis cutis/pulmonitis, inflammatory breast disease, and abdominal masses (not followed by CT or MRI), are considered as non-measurable.

Note: Cystic lesions that meet the criteria for radiographically defined simple cysts should not be considered as malignant lesions (neither measurable nor non-measurable) since they are, by definition, simple cysts.

'Cystic lesions' thought to represent cystic metastases can be considered as measurable lesions, if they meet the definition of measurability described above. However, if non-cystic lesions are present in the same subject, these are preferred for selection as target lesions.

**8.1.1.3.** *Malignant lymph nodes*. To be considered pathologically enlarged and measurable, a lymph node must be ≥15 mm in short axis when assessed by CT scan (CT scan slice thickness recommended to be no greater than 5 mm). At baseline and in follow-up, only the short axis will be measured and followed.

# 8.1.1.4. Baseline documentation of "Target" and "Non-Target" lesions:

Target lesions. All measurable lesions up to a maximum of 2 lesions per organ and 5 lesions in total, representative of all involved organs, should be identified as target lesions and recorded and measured at baseline. Target lesions should be selected on the basis of their size (lesions with the longest diameter), be representative of all involved organs, but in addition should be those that lend themselves to reproducible repeated measurements. It may be the case that, on occasion, the largest lesion does not lend itself to reproducible measurement in which circumstance the next largest lesion which can be measured reproducibly should be selected. A sum of the diameters (longest for non-nodal lesions, short axis for nodal lesions) for all target lesions will be calculated and reported as the baseline sum diameters. If lymph nodes are to be included in the sum, then only the short axis is added into the sum. The baseline sum diameters will be used as reference to further characterize any objective tumor regression in the measurable dimension of the disease.

**Non-target lesions**. All other lesions (or sites of disease) including any measurable lesions over and above the 5 target lesions should be identified as **non-target lesions** and should also be recorded at baseline. Measurements of these lesions are not required, but the presence, absence, or in rare cases unequivocal progression of each should be noted throughout follow-up.

# 8.2. Response Criteria for Target Lesions –RECIST version 1.1

**8.2.1.** Evaluation of target lesions

Complete Response (CR)	Disappearance of all target lesions. Any pathological
	lymph nodes (whether target or non-target) must
	have reduction in short axis to <10 mm.
Partial Response (PR)	At least a 30% decrease in the sum of the diameters
	of target lesions, taking as reference the baseline sum
	diameters
Progressive Disease (PD)	At least a 20% increase in the sum of the diameters
	of target lesions, taking as reference the smallest sum
	on study (this includes the baseline sum if that is the
	smallest on study). In addition to the relative
	increase of 20%, the sum must also demonstrate an
	absolute increase of at least 5 mm. (Note: the
	appearance of one or more new lesions is also
	considered progressions).

Stable Disease (SD)	Neither sufficient shrinkage to qualify for PR nor
	sufficient increase to qualify for PD, taking as
	reference the smallest sum diameters while on study

8.2.2. Evaluation of non-target lesions

Response Criteria	Evaluation of non-target lesions
* Complete Response (CR)	Disappearance of all non-target lesions
	and normalization of tumor marker
	level
* Incomplete Response/ Stable Disease (SD)	Persistence of one or more non-target
	lesion(s) or/and maintenance of tumor
	marker level above the normal limits
* Progressive Disease (PD)	Appearance of one or more new lesions
	and/or unequivocal progression of
	existing non-target lesions*

\* Although a clear progression of "non-target" lesions only is exceptional, the opinion of the treating physician should prevail in such circumstances, and the progression status should be confirmed at a later time by the Sponsor-Investigator.

#### 8.3. Evaluation of best overall response –RECIST version 1.1

The best overall response is the best response recorded from the start of the treatment until disease progression/recurrence (taking as reference for PD the smallest measurements recorded since the treatment started). In general, the subject's best response assignment will depend on the achievement of both measurement and confirmation criteria.

Non-Target Lesions	New Lesions	Overall Response
CR	No	CR
Non-CR/ Non-PD	No	PR
Not evaluated	No	PR
Non-PD/ or not all evaluated	No	PR
Non-PD or not all evaluated	No	SD
Non-PD	No	Non-evaluable
Any	Yes or No	PD
PD*	Yes or No	PD
Any	Yes	PD
	CR Non-CR/ Non-PD Not evaluated Non-PD/ or not all evaluated Non-PD or not all evaluated Non-PD Any PD* Any Any	CR No Non-CR/Non-PD No Not evaluated No Non-PD/ or not all evaluated No Non-PD or not all evaluated No Non-PD No Any Yes or No PD* Yes or No

\*In exceptional circumstances, unequivocal progression in non-target lesions may be accepted as disease progression.

Subjects with a global deterioration of health status requiring discontinuation of treatment without objective evidence of disease progression at that time should be classified as having "symptomatic deterioration." Every effort should be made to document the objective progression even after discontinuation of treatment.

In some circumstances it may be difficult to distinguish residual disease from normal tissue. When the evaluation of complete response depends on this determination, it is recommended

that the residual lesion be investigated (fine needle aspirate/biopsy) to confirm the complete response status.

# 8.4. Definitions for Response Evaluation –RECIST version 1.1

## **8.4.1.** First Documentation of Response:

The time between initiation of therapy and first documentation of PR or CR.

# **8.4.2.** Confirmation of Response:

To be assigned a status of complete or partial response, changes in tumor measurements must be confirmed by repeat assessments performed no less than four weeks after the criteria for response are first met.

# **8.4.3.** Duration of Response:

Duration of overall response—the period measured from the time that measurement criteria are met for complete or partial response (whichever status is recorded first) until the date that recurrent or progressive disease is objectively documented (taking as reference for progressive disease the smallest measurements recorded since treatment started).

# 8.4.4. Duration of Overall Complete Response:

The period measured from the time that measurement criteria are met for complete response until the first date that progressive disease is objectively documented.

## 8.4.5. Objective response rate:

The objective response rate is the proportion of all subjects with confirmed PR or CR according to RECIST v1.1 from the start of treatment until disease progression/recurrence (taking as reference for progressive disease the smallest measurements recorded since the start of treatment).

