# 2.1.2. Secondary Objectives

- Characterize safety and tolerability of palbociclib and tamoxifen in first line therapy for subjects with HR(+)/HER2(-) advanced breast cancer who have not received prior systemic anti-cancer therapies for their advanced/metastatic disease.
- Evaluate response rates (complete or partial response) (RR) per local assessment and RECIST 1.1 or MDA criteria in subjects with HR(+)/HER2(-) advanced breast cancer who have not received prior systemic anti-cancer therapies for their advanced/metastatic disease treated with palbociclib in combination with tamoxifen.
- Evaluate clinical benefit rate RR (complete, partial response, or stable disease, lasting 24 weeks or longer) based on RECIST 1.1 or MDA criteria in subjects with HR(+)/HER2(-) advanced breast cancer who have not received prior systemic anti-cancer therapies for their advanced/metastatic disease treated with palbociclib in combination with tamoxifen.
- Measure overall survival (OS) at 2 years in subjects with HR(+)/HER2(-) advanced breast cancer who have not received prior systemic anti-cancer therapies for their advanced/metastatic disease treated with palbociclib in combination with tamoxifen.

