#### 3.1. Inclusion Criteria

Subjects must meet all of the following applicable inclusion criteria to participate in this study:

**3.1.1** Male or female  $\geq$  18 years of age at time of consent.

**NOTE**: Both pre- and post-menopausal women are eligible.

Pre-menopausal status is defined as either:

- -Last menstrual period within the last 12 months
- -In case of therapy-induced amenorrhea, plasma estradiol and /or FSH is in the premenopausal range per local normal range.
- **3.1.2** Locally advanced, locoregionally recurrent, or metastatic disease, not amenable to curative therapy. **NOTE**: Although not required as a protocol procedure, a patient with a new metastatic lesion should be considered for biopsy whenever possible to reassess ER/PR/HER2 status if clinically indicated. If a biopsy is prospectively done as part of standard of care, the study would like to store samples for correlative research.
- **3.1.3** Histologically and/or cytologically confirmed diagnosis of ER positive and/or PR positive (ER >1%, PR >1%), HER2 negative breast cancer.

**NOTE**: Subject has HER2-negative breast cancer (based on most recently analyzed biopsy) is defined as a negative in situ hybridization test or an IHC status of 0, 1+ or 2+. If IHC is 2+, a negative in situ hybridization (e.g. FISH, CISH, SISH, DISH, etc.) test is required by local laboratory testing.

**3.1.4** Metastatic disease evaluable on imaging studies. Subjects may have measurable disease as per RECIST 1.1 or bone-only disease.

**NOTE**: Bone-only subjects are eligible if their disease can be documented/ evaluated by bone scans, CT or MRI. Their disease will be assessed using MDA criteria.

**NOTE**: Previously irradiated lesions are eligible as a target lesion only if there is documented progression of the lesion after irradiation.

**3.1.5** No prior systemic anti-cancer therapy for advanced HR+ disease.

**NOTE**: Subjects receiving adjuvant treatment with aromatase inhibitors at time of recurrence are allowed to participate. There is no AI washout period required.

- **3.1.6** Eastern Cooperative Oncology Group (ECOG) Performance Status 0-2
- **3.1.7** Adequate hepatic function within 14 days prior to registration for protocol therapy defined as meeting **all** of the following criteria:
  - aspartate aminotransferase (AST)  $\leq$  2.5 × ULN or  $\leq$  5 × ULN for subjects with known hepatic metastases and

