# 8.6. Response Criteria for MD Anderson (MDA) Criteria (21)

Complete Response (CR)	Complete sclerotic fill-in of lytic lesions on XR or CT
	Normalization of bone density on XR or CT
	Normalization of signal intensity on MRI
	Normalization of tracer uptake on SS
Partial Response (PR)	Development of a sclerotic rim or partial sclerotic fill-in of lytic lesions on XR or CT
	Osteoblastic flare - Interval visualization of lesions with sclerotic rims or new sclerotic lesions in the setting of other signs of PR and absence of progressive bony disease
	• ≥ 50% decrease in measurable lesions on XR, CT, or MRI
	• ≥ 50% subjective decrease in the size of ill-defined lesions on XR, CT, or MRI
	• $\geq 50\%$ subjective decrease in tracer uptake on SS
Progressive Disease (PD)	• > 25% increase in size of measurable lesions on XR, CT, or MRI
	• > 25% subjective increase in the size of ill-defined lesions on XR, CT, or MRI
	• > 25% subjective increase in tracer uptake on SS
	New bone metastases
Stable Disease (SD)	No change
	• < 25% increase or < 50% decrease in size of measurable
	lesions
	• < 25% subjective increase or < 50% subjective decrease in size of ill-defined lesions
	No new bone metastases
	y; CT: computed tomography; SS: skeletal scintigraphy; MRI:
magnetic resonance imaging.	

Measurements are based on the sum of a perpendicular, bi-dimensional measurement of the greatest diameters of each individual lesion.

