### 12.5. Analysis of Secondary Endpoints

Characterize safety and tolerability of palbociclib and tamoxifen in first line therapy for subjects with HR(+)/HER2(-) advanced breast cancer who have not received prior systemic anti-cancer therapies for their advanced/metastatic disease.

 Proportion of subjects with each grade of adverse events as defined by CTCAE v4 will be computed along with 95% confidence intervals, and reported in a tabular and descriptive manner.

Assess response rate based on RECIST 1.1 or MDA Criteria. The response rate (complete or partial response) and 95% confidence interval for the response rate will be computed using PROC FREQ in SAS (Cary, NC).

Evaluate clinical benefit rate RR (complete, partial response, or stable disease) based on RECIST 1.1 or MDA Criteria in subjects with HR(+)/HER2(-) advanced breast cancer who have not received prior systemic anti-cancer therapies for their advanced/metastatic disease treated with palbociclib in combination with tamoxifen.

• Clinical benefit rate (complete, partial response, or stable disease) will be assessed every 8 weeks +/- 1 week while on study treatment using RECIST 1.1 (section 8) or MDA Criteria (for patients with bone only disease). Response will be recorded as disease control rate (DCR), or stable disease plus partial response plus complete response, and reported via waterfall plot. The response rate and 95% confidence interval for the response rate will be computed using PROC FREQ in SAS (Cary, NC).

Measure 2-year overall survival (OS) in subjects with HR(+)/HER2(-) advanced breast cancer who have not received prior systemic anti-cancer therapies for their advanced/metastatic disease treated with palbociclib in combination with tamoxifen.

Median OS times will be computed, and OS rate will be calculated with associated 95% confidence intervals. Kaplan-Meier curves will be plotted. Data will be analyzed using the PROC FREQ and PROC LIFETEST in SAS.

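### Section 8.4.5 keeps bone-only subjects in the response-rate denominator but leaves out their MDA responses, against 2.1.2, section 8 and 12.5; no confirmation rule is stated for MDA responses

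*Combined protocol and SAP*

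**What the plan says.** The protocol gives two accounts of response.

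- Section 8.4.5: "The objective response rate is the proportion of all subjects with confirmed PR or CR according to RECIST v1.1". It is the only place that gives both a numerator and a denominator.
- Section 2.1.2 sets the secondary objective: "Evaluate response rates (complete or partial response) (RR) per local assessment and RECIST 1.1 or MDA criteria". Section 12.5 repeats it: "Assess response rate based on RECIST 1.1 or MDA Criteria". The synopsis agrees.
- The opening of section 8 assigns the criteria: "Response assessments for subjects with bone only disease will be made using MDA criteria". Visceral disease, with or without bone disease, goes to RECIST 1.1.
- Section 3.1.4 admits both kinds of subject: "Subjects may have measurable disease as per RECIST 1.1 or bone-only disease". No cap or expected share of bone-only subjects is given.
- Section 8.1.1.2 lists what is non-measurable, beginning "Bone lesions, leptomeningeal disease, ascites, pleural/pericardial effusions".
- Section 8.4.2, under a heading limited to RECIST 1.1, requires that "changes in tumor measurements must be confirmed by repeat assessments performed no less than four weeks after the criteria for response are first met".
- Section 8.6 defines MDA response. Partial response includes "Development of a sclerotic rim or partial sclerotic fill-in of lytic lesions on XR or CT", subjective falls of at least 50% in lesion size or tracer uptake, and a fall of at least 50% in measurable lesions. It has no confirmation rule.
- Section 12.2 defines Enrolled, Evaluable and Safety populations and leaves the choice for each analysis to the protocol. Section 12.5 assigns none to the response rate.

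**The concern.** A bone-only subject whose lesions respond under MDA is a responder under 12.5. Under 8.4.5 the same subject is in the denominator and not in the numerator. Two analysts working from the two sections would report different response rates from the same data, each able to cite the protocol.

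Responder status is also used elsewhere. The correlative work in section 9, if funded, compares responders with non-responders and compares response between subgroups. If the bone-only share differed between subgroups, 8.4.5 would show a difference in response even where the response rate under the assigned criteria was the same.

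Confirmation is a second gap. The RECIST rule speaks of tumor measurements, whereas several MDA partial-response items are changes in bone appearance or uptake. The text does not say whether those need a second assessment.

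**Working it through.** **The plan's own figure.** The documents give no target, expected value or precision for the response rate. The only planned figure is N = 48 for PFS (12.3), and it reproduces:

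- events = (1.645 + 0.842)² / [ln(15/25)]² = 23.7;
- probability of an event under the 25-month median, with 24 months of uniform accrual and 24 more months of follow-up = 0.625;
- 23.7 / 0.625 = 37.9, and 37.9 / (1 − 0.20) = 47.4, rounded up to 48.

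The response rate does not enter this calculation.

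**Notation.** Let b be the bone-only share, r the confirmed RECIST response rate in all other subjects, and m the MDA response rate in bone-only subjects. None of the three is in the documents. Everyone who is not bone-only is taken as RECIST-assessed, and a RECIST complete response in bone-only disease is neglected.

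- Rate under 8.4.5 = (1 − b)r
- Rate under 12.5 = (1 − b)r + bm
- Difference = bm, whatever r is

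**Range.** Assume b = 0.15 to 0.30, m = 0.20 to 0.60 and, for illustration, r = 0.40.

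| b | 8.4.5 | 12.5 at m = 0.20 | 12.5 at m = 0.60 | Difference |
|---|---|---|---|---|
| 0.15 | 0.85 × 0.40 = 34% | 34 + 3 = 37% | 34 + 9 = 43% | 3 to 9 points |
| 0.30 | 0.70 × 0.40 = 28% | 28 + 6 = 34% | 28 + 18 = 46% | 6 to 18 points |

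In subjects: 0.03 × 48 = 1.4, and 0.18 × 48 = 8.6. With wider assumptions (b = 0.10 to 0.40, m = 0.10 to 0.50) the difference runs from 0.10 × 0.10 = 1 point to 0.40 × 0.50 = 20 points.

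**Example in whole subjects.** Take 48 subjects, 14 of them bone-only with 7 MDA responders (m = 0.50), and 10 responders among the other 34 (r about 0.30). Intervals are Clopper-Pearson 95%.

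- 8.4.5: 10/48 = 20.8% (10.5 to 35.0)
- 12.5: 17/48 = 35.4% (22.2 to 50.5)
- RECIST-assessed subjects only: 10/34 = 29.4% (15.1 to 47.5)

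**What each rate depends on.** Both rise with r, by 1 − b points per point: 0.85 to 0.70 over the 15-30% range. The 8.4.5 rate is always diluted by the factor 1 − b. The 12.5 rate depends on b only when m and r differ: at m = r = 0.40 it is 40% for every b.

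**The case against.** The best defence is that the protocol already says who is judged by what. Section 8 assigns the criteria at its start, and the synopsis, 2.1.2, 3.1.4 and 12.5 agree with it. Section 8.4.5 lies under a RECIST-only heading and uses the term objective response rate, where the objectives and 12.5 say response rate. On this view it is one line not carried through. That is probably how the conflict arose, and it points to the intended reading. It does not remove the conflict, because the line says all subjects and no other section supplies a denominator.

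A reader might also infer more than the documents support:

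- *That bone-only subjects can never respond under RECIST.* A partial response needs target lesions, which they lack, but 8.2.2 allows a complete response through disappearance of non-target lesions.
- *That MDA responses are counted unconfirmed.* The text is silent. Scheduled imaging every two cycles up to cycle 19 and every three from cycle 22, with repeat bone scans where the screening scan was positive, could supply confirmation.
- *That the rate tracks the bone-only share rather than drug activity.* The formulas show that both rates move with activity, and that the 12.5 rate need not move with the share at all.
- *That the rate loses comparability with the 25-30% tamoxifen response rate in section 1.1.* No such comparison is planned, and how the cited source handled bone-only disease cannot be seen from these documents.

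It is also fair to say that the size is wholly assumed and that its upper end needs both inputs at their maximum.

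**Conclusion.** The conflict is in the text and should be resolved before analysis. Followed as written, 8.4.5 counts MDA responders with bone-only disease as non-responders, and its rate falls short of the 12.5 rate by bm. That is 3 to 18 percentage points on the assumed 15-30% share and 20-60% MDA rate; it is zero if no bone-only subject enrols or none responds by MDA. The missing MDA confirmation rule and the unassigned analysis population are further gaps in the same definition.

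The consequence is limited. The endpoint is secondary and descriptive, with no hypothesis or power attached, and neither the PFS analysis nor N = 48 changes. Nor does the finding require the pooled RECIST-or-MDA rate to be demoted: the objectives name it, and it is a legitimate summary if the stratum rates stand beside it.

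**What to change.** 1. Reconcile 8.4.5 with 2.1.2 and 12.5 so that one definition applies: response by the criteria that section 8 assigns to the subject, divided by a named analysis population from 12.2.
2. State whether the four-week confirmation in 8.4.2 also applies to MDA responses.
3. Report, each with a 95% confidence interval, the pooled rate, the RECIST rate among RECIST-assessed subjects (and among those with measurable disease at baseline), and the MDA rate among bone-only subjects.

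The cost is wording in 8.4.5 and 12.5 and a few more table rows; no extra subjects are needed. The stratum rates will be less precise. At a 40% rate the Wald half-width 1.96 × √(0.24/n) is 13.9 points at n = 48, 15.0 at n = 41 (15% bone-only) and 16.5 at n = 34 (30% bone-only). The bone-only stratum of 7 to 14 subjects will be imprecise: at a 50% rate, 1.96 × √(0.25/14) is about 26 points and 1.96 × √(0.25/7) about 37. Its rate should therefore be read as descriptive only.
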